8 ADVERSE EVENTS: DEFINITIONS AND REPORTING REQUIREMENTS

8.1 Definitions

8.1.1 Adverse Event (AE)

AE means any untoward medical occurrence associated with the use of a drug in humans, whether or not considered drug related.

8.1.2 Serious AE (SAE)

An AE is considered “serious” if, in the view of either the investigator or sponsor, it results in any of the following outcomes:

- death,
- a life-threatening AE (An AE is considered “life-threatening” if, in the view of either the investigator or sponsor, its occurrence places the patient or subject at immediate risk of death. It does not include an AE that, had it occurred in a more severe form, might have caused death.),
- inpatient hospitalization or prolongation of existing hospitalization,
- a persistent or significant incapacity or substantial disruption of the ability to conduct normal life functions, or
- a congenital anomaly/birth defect.

Important medical events that may not result in death, be life-threatening, or require hospitalization may be considered serious when, based upon appropriate medical judgment, they may jeopardize the patient or subject and may require medical or surgical intervention to prevent one of the outcomes listed in this definition.

8.1.3 Unanticipated Problem (UP)

Unanticipated problems include any incident, experience, or outcome that meets all of the following criteria:

- unexpected (in terms of nature, severity, frequency) given (a) the research procedures that are described in the protocol-related documents, such as the

IRB-approved research protocol and informed consent document; and (b) the characteristics of the subject population being studied;

- related or possibly related to participation in the research (possibly related means there is a reasonable possibility that the incident, experience, or outcome may have been caused by the procedures involved in the research); and
- suggests that the research places subjects or others at a greater risk of harm (including physical, psychological, economic, or social harm) than was previously known or recognized.

8.1.4 AE Description and Grade

The descriptions and grading scales found in the revised Common Terminology Criteria for Adverse Events (CTCAE) version 5.0 will be utilized for AE reporting.

8.1.5 AE Expectedness

AEs can be 'Unexpected' or 'Expected'.

Expected AEs are listed in Section [8.2](#) below.

Unexpected AEs are those AEs occurring in one or more subjects participating in the research protocol, the nature, severity, or frequency of which is not consistent with either:

- The known or foreseeable risk of AEs associated with the procedures involved in the research that are described in (a) the protocol-related document, such as the IRB-approved research protocol, any applicable investigator brochure, and the current IRB-approved informed consent document, and other relevant sources of information, such as product labeling and package inserts; or
- The expected natural progression of any underlying disease, disorder, or condition of the subject(s) experiencing the AE and the subject's predisposing risk factor profile for the AE.

8.1.6 AE Attribution

- Definite – The AE *is clearly related* to the study treatment.
- Probable – The AE *is likely related* to the study treatment.
- Possible – The AE *may be related* to the study treatment.
- Unlikely – The AE *is doubtfully related* to the study treatment.
- Unrelated – The AE *is clearly NOT related* to the study treatment.

8.2 Known AEs List

See Section [9.2.11](#)

8.3 Time Period and Grade of AE Capture

All AEs, SAEs, and UPs will be captured as follows and recorded in the study database.

All AEs, SAEs, and UPs will be evaluated from the time the informed consent form is signed through the follow-up visit 30 ± 15 days after the last administered component of study regimen (see Section [6.5.1](#)). The AE safety follow-up period may be truncated if the patient begins other antineoplastic therapy during that time. Collection of irAEs will continue at survival status assessment time points (every 3 months ± 15 days) as long as survival status assessment continues.

8.4 Procedures for Recording AEs, SAEs, and UPs

- AEs, SAEs, UPs, and other reportable events will be recorded in MCC's OnCore Clinical Trials Management System.
- In most cases, it is acceptable to record in OnCore only the highest grade of a toxicity occurring during a particular study segment when an event has serial fluctuations in grade over time.
- SAEs will be entered into the OnCore SAE domain. UPs will be entered into the OnCore Deviations domain. An SAE that is both an SAE and a UP will be entered in both domains.
- AEs requiring expedited reporting must also be recorded by routine AE capture (i.e., in AE eCRFs).

8.5 Expedited Reporting Procedures

Table 5. Expedited Reporting Requirements for Participating Sites

SAEs	UPs	Qualifying Toxicities
Principal Investigator ¹ [name] [REDACTED] [REDACTED]	Principal Investigator ¹ [name] [REDACTED] [REDACTED]	Principal Investigator ¹ [name] [REDACTED]
Coordinating Center ¹ Investigator-Initiated Trials Research Operations (IITRO) [REDACTED] [REDACTED]	Coordinating Center ¹ Investigator-Initiated Trials Research Operations (IITRO) [REDACTED] [REDACTED]	Coordinating Center ¹ Investigator-Initiated Trials Research Operations (IITRO) [REDACTED] [REDACTED]
IRB (if applicable) ²	IRB ²	

¹ Report event within 1 business days of becoming aware of the occurrence. A PDF of a de-identified Oncore Deviation record may be used for expedited event reporting purposes.

² Report SAEs and UPs to the IRB of record according to local institutional guidelines.

Table 6. Expedited Reporting Requirements for Coordinating Center

UPs
DSMC¹
IRB²
¹ Report to DSMC within 2 business days of becoming aware of the occurrence. A PDF of a de-identified Oncore Deviation record may be used for expedited event reporting purposes.
² Report to the VCU IRB within 5 business days of becoming aware of the occurrence.

[figure not shown]

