9.2.11 Adverse Events

The safety of pembrolizumab in combination with lenvatinib (20 mg orally once daily) was investigated in KEYNOTE-146, a single-arm, multicenter, open-label trial in 94 patients with endometrial carcinoma whose tumors had progressed following one line of systemic therapy and were not MSI-H or dMMR. The median duration of study treatment was 7 months (range: 0.03 to 37.8 months). The median duration of exposure to pembrolizumab was 6 months (range: 0.03 to 23.8 months).

Pembrolizumab was continued for a maximum of 24 months; however, treatment with lenvatinib could be continued beyond 24 months. Fatal adverse reactions occurred in 3% of patients receiving pembrolizumab and lenvatinib, including gastrointestinal perforation, reversible posterior leukoencephalopathy syndrome (RPLS) with intraventricular hemorrhage, and intracranial hemorrhage. Serious adverse reactions occurred in 52% of patients receiving pembrolizumab and lenvatinib.

Serious adverse reactions in $\geq 3\%$ of patients were hypertension (9%), abdominal pain (6%), musculoskeletal pain (5%), hemorrhage (4%), fatigue (4%), nausea (4%), confusional state (4%), pleural effusion (4%), adrenal insufficiency (3%), colitis (3%), dyspnea (3%), and pyrexia (3%). Pembrolizumab was discontinued for adverse reactions (grade 1-4) in 19% of patients, regardless of action taken with lenvatinib.

The most common adverse reactions ($\geq 2\%$) leading to discontinuation of pembrolizumab were adrenal insufficiency (2%), colitis (2%), pancreatitis (2%), and muscular weakness (2%).

Adverse reactions leading to interruption of pembrolizumab occurred in 49% of patients; the most common adverse reactions leading to interruption of pembrolizumab ($\geq 2\%$) were: fatigue (14%), diarrhea (6%), decreased appetite (6%), rash (5%), renal impairment (4%), vomiting (4%), increased lipase (4%), weight loss (4%), nausea (3%), increased blood alkaline phosphatase (3%), skin ulcer (3%), adrenal insufficiency (2%), increased amylase (2%), hypocalcemia (2%), hypomagnesemia (2%), hyponatremia (2%), peripheral edema (2%), musculoskeletal pain (2%), pancreatitis (2%), and syncope (2%). [Table 7](#) and

Table 8 summarize adverse reactions and laboratory abnormalities, respectively, in patients on pembrolizumab in combination with lenvatinib.

Table 7. Adverse Reactions Occurring in $\geq 20\%$ of Patients with Endometrial Carcinoma in KEYNOTE-146

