14 DATA AND SAFETY MONITORING PLAN (DSMP)

While patients are on treatment, the principal investigator, study team members (e.g., site investigators, research nurses, clinical research associates) and Coordinating Center staff will meet at least monthly to review study status. The biostatistician will review data with the principal investigator and Coordinating Center staff at least quarterly. This review will include, but not be limited to, reportable events and an update of the ongoing study summary that describes study progress in terms of the study schema. All meetings, including attendance, are documented.

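### By default, a treatment-related death from a listed fatal reaction has no expedited route to the DSMC

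*Combined protocol and SAP*

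**What the plan says.** Section 8.5 sets up expedited reporting in two tables.

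- **Table 5 (sites)** has three columns: SAEs, UPs and "Qualifying Toxicities". All three go to the principal investigator and the Coordinating Center: "Report event within 1 business days of becoming aware of the occurrence". SAEs also go to the IRB where applicable and UPs go to the IRB, in both cases under local guidelines. The DSMC is not a recipient.
- **Table 6 (Coordinating Center)** has one column, UPs. For the DSMC the instruction is "Report to DSMC within 2 business days of becoming aware of the occurrence". The VCU IRB is allowed 5 business days.

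Section 8.1.3 defines a UP by a joint test: "Unanticipated problems include any incident, experience, or outcome that meets all of the following criteria". The first criterion is that the event be "unexpected (in terms of nature, severity, frequency) given (a) the research procedures that are described in the protocol-related documents" and given the population studied. The second is that it be related or possibly related, and the third that it suggest greater risk than previously recognized.

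On expectedness, 8.1.5 begins "Expected AEs are listed in Section" and names 8.2, which contains only a pointer to 9.2.11. There one reads: "Fatal adverse reactions occurred in 3% of patients receiving pembrolizumab and lenvatinib, including gastrointestinal perforation". The other two causes named are RPLS with intraventricular hemorrhage and intracranial hemorrhage.

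Section 14.1.2 has the DSMC review the study on a schedule set by risk level and then by study status and quality. It gives no interval. Section 14 also provides study-team meetings at least monthly, and "The biostatistician will review data with the principal investigator and Coordinating Center staff at least quarterly".

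**The concern.** The DSMC is the body charged with looking at patient safety from outside the study team. Under these tables the most serious known harms of the regimen are the ones least likely to reach it promptly, because the filter for prompt notice is unexpectedness and the known fatal reactions sit inside the list of expected events.

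This matters more here than in a trial that repeats its reference population. Section 3.1 describes Black patients as under-represented in the two registration trials. The reference patients in 9.2.11 had progressed after one line of systemic therapy, whereas 4.1.5 allows two prior lines and prior checkpoint inhibitor treatment. A fatal rate seen in 94 somewhat different patients is weak ground for treating a related death in this trial as routine.

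**Working it through.** The plan states no figure for this point, so the main check is to follow one event through the text. Take a death from gastrointestinal perforation judged at least possibly related to treatment.

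1. **Is it an SAE?** Yes: death is a listed outcome in 8.1.2. Table 5 sends it to the principal investigator and Coordinating Center within 1 business day, and to the IRB of record if local rules call for it.
2. **Does Table 6 carry it further?** Only if it is a UP. Section 16.1 adds no other route; for SAE and UP reporting it refers back to Section 8.
3. **Is it a UP?** It meets the relatedness criterion. On unexpectedness, 8.1.5, 8.2 and 9.2.11 together describe this event, with this outcome, at a stated frequency. A single case is consistent with all three. On greater risk, one case at a listed rate does not by itself suggest more than was known. Since all three criteria must hold, the default answer is no.
4. **What remains?** The routine DSMC review in 14.1.2, at an unstated interval. The monthly and quarterly meetings in Section 14 are internal to the study team, biostatistician and Coordinating Center.

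The same holds for the other two named causes. It may hold more widely, since 8.1.5 also counts consistency with product labeling, and 9.1.9 and 9.2.10 mention fatal cardiac dysfunction, renal failure, hemorrhage and immune-mediated reactions.

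**How often would this arise?** Inputs: N = 100 (3.1, an upper limit); fatal rate p = 3% in 94 patients (9.2.11). The count behind 3% is inferred: 2/94 = 2.1%, 3/94 = 3.2% and 4/94 = 4.3%, so only 3 rounds to 3%. The exact (Clopper-Pearson) 95% interval for 3/94 is 0.7% to 9.0%.

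Expected number = N × p; chance of at least one = 1 − (1 − p)^N.

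| Rate p | Expected in 100 | Chance of at least one |
|---|---|---|
| 1% (assumed) | 1.0 | 1 − 0.99^100 = 63.4% |
| 3% (9.2.11) | 3.0 | 1 − 0.97^100 = 95.2% |
| 5% (assumed) | 5.0 | 1 − 0.95^100 = 99.4% |

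**How much help is the frequency criterion?** At a true rate of 3%, the binomial probability of 5 or more fatal reactions in 100 is 18.2%, and of 7 or more 3.1%. A total of 5 would therefore still be unremarkable against the listed rate. Frequency can bring a cluster to the DSMC, but it will not ordinarily bring the first few deaths.

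**The case against.** The strongest reply is that UP-only expedited reporting to a DSMC is a defensible choice for this regimen. Both drugs are commercially available and described as standard of care (9.1.5, 9.2.6), and Section 1.3 records FDA approval of the combination for this disease. The DSMC also receives Compliance Office reports as well as the study team's (14.1.2), and its schedule is delegated to an institutional process rather than absent. All of this is true. It lowers the urgency but does not supply a prompt route for related deaths.

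A reader might infer more than the text supports:

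- *That such deaths are hidden from anyone independent, or that an excess is judged by the investigators alone.* The IRB of record may hear of an SAE under local rules, and the DSMC sees the data at routine review. The gap is in timing.
- *That a listed cause can never be a UP.* Sections 8.1.3 and 8.1.5 allow severity or frequency to make an event unexpected, and 8.1.3 adds the characteristics of the population. No numerical threshold is needed; it is a judgement. The bypass is a default, not a certainty.
- *That the Qualifying Toxicities column leads nowhere.* It reaches the principal investigator and Coordinating Center in 1 business day. What is missing is a definition and any step beyond them. The schema and revision-history pages are not legible in the public copy, so a definition there cannot be wholly excluded.
- *That the number of patients enrolled between DSMC reviews can be computed.* The quarterly interval in Section 14 belongs to the internal meeting; the DSMC's own interval is not stated.

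**Conclusion.** The concern holds as a gap in timing and routing. By default, a related death from a cause listed in 9.2.11 gets no 2-business-day notice to the DSMC and waits for a routine review of unstated interval. Only a judgement by the study team that its severity or frequency is unexpected changes that.

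If the 3% rate carries over, about 3 fatal reactions would occur in 100 patients, with a 95% chance of at least one; over assumed rates of 1% to 5% that chance is 63% to 99%. These figures assume full enrollment of 100, independent patients, and that the 3% applies to this population, which the protocol cannot yet know. They also count all fatal reactions in the 3%, not each named cause separately. The routing conclusion depends on none of these assumptions. It rests on reading the whole of 9.2.11 as the expected list, which is what 8.2 says.

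The change is worth making, but the gap does not undermine the trial. The undefined Qualifying Toxicities column is a smaller drafting matter.

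**What to change.** Add a row to Table 6: any death at least possibly related to study treatment (possible, probable or definite under 8.1.6), expected or not, goes to the DSMC within the existing 2 business days. The sponsor may extend the row to related life-threatening SAEs.

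As tidying, define Qualifying Toxicities in 8.1 and give its onward route, or delete the column from Table 5.

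The cost is about 3 extra death reports over the trial at 3% (1 at 1%, 5 at 5%). If life-threatening events are included, there would be further reports whose number the documents do not allow one to estimate. Keeping the row to these events limits the burden: 9.2.11 gives a 52% rate of serious adverse reactions, so sending every SAE would involve about 0.52 × 100 = 52 patients. No numerical review trigger is needed for this fix; whether to adopt one can be left to the DSMC. The change affects reporting only, not treatment.

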9 PHARMACEUTICAL INFORMATION

9.1 Lenvatinib (Lenvima)

The following information is based on the Prescribing Information for Lenvima (lenvatinib) dated July 2021.

9.1.1 Product Description

Lenvatinib, a kinase inhibitor, is the mesylate salt of lenvatinib. Its chemical name is 4-[3-chloro-4-(N'-cyclopropylureido)phenoxy]-7-methoxyquinoline-6-carboxamide methanesulfonate. The molecular formula is C₂₁H₁₉CIN₄O₄ • CH₄O₃S, and the molecular weight of the mesylate salt is 522.96. The chemical structure of lenvatinib mesylate is:

Lenvatinib mesylate is a white to pale reddish yellow powder. It is slightly soluble in water and practically insoluble in ethanol (dehydrated). The dissociation constant (pKa value) of lenvatinib mesylate is 5.05 at 25°C. The partition coefficient (log P value) is 3.3.

Lenvima capsules for oral administration contain 4 mg or 10 mg of lenvatinib, equivalent to 4.90 mg or 12.25 mg of lenvatinib mesylate, respectively. The inactive ingredients are: calcium carbonate, hydroxypropyl cellulose, low-substituted hydroxypropyl cellulose, mannitol, microcrystalline cellulose, and talc.

In addition, the capsule shell contains ferric oxide red, ferric oxide yellow, hypromellose, and titanium dioxide. The printing ink contains black iron oxide, potassium hydroxide, propylene glycol, and shellac.

9.1.2 Mechanism of Action

Lenvatinib is a kinase inhibitor that inhibits the kinase activities of vascular endothelial growth factor (VEGF) receptors VEGFR1 (FLT1), VEGFR2 (KDR), and

VEGFR3 (FLT4). Lenvatinib inhibits other kinases that have been implicated in pathogenic angiogenesis, tumor growth, and cancer progression in addition to their normal cellular functions, including fibroblast growth factor (FGF) receptors FGFR1, 2, 3, and 4; platelet derived growth factor receptor alpha (PDGFR α), KIT, and RET. Lenvatinib also exhibited antiproliferative activity in hepatocellular carcinoma cell lines dependent on activated FGFR signaling with a concurrent inhibition of FGF-receptor substrate 2 α (FRS2 α) phosphorylation.

In syngeneic mouse tumor models, lenvatinib decreased tumor-associated macrophages, increased activated cytotoxic T cells, and demonstrated greater antitumor activity in combination with an anti-PD-1 monoclonal antibody compared to either treatment alone.

9.1.3 Storage and Handling Requirements

Lenvatinib 4-mg capsules are supplied as hard hypromellose capsules with yellowish-red body and yellowish-red cap, marked in black ink with “E” on the cap and “LENV 4 mg” on the body.

Lenvatinib 10 mg capsules are supplied as hard hypromellose capsules with yellow body and yellowish-red cap, marked in black ink with “E” on the cap and “LENV 10 mg” on the body.

Lenvatinib capsules are supplied in cartons of 6 cards.

Store at 25°C (77°F); excursions permitted to 15 – 30°C (59 – 86°F)

9.1.4 Administration

Oral.

Reduce the dose for certain patients with renal or hepatic impairment.

Take lenvatinib once daily, with or without food, at the same time each day. If a dose is missed and cannot be taken within 12 hours, skip that dose and take the next dose at the usual time of administration.

The recommended dosage of lenvatinib is 20 mg orally once daily, in combination with pembrolizumab 200 mg administered as an intravenous infusion over 30 minutes every 3 weeks, until unacceptable toxicity or disease progression.

9.1.5 Availability and Ordering

Lenvatinib is commercially available and administration is standard of care for patients with endometrial cancer. The costs of lenvatinib and its administration will be the responsibility of the patient and/or the patient’s 3rd party payor.

9.1.6 Contraindications

No contraindications have been identified.

9.1.7 Pharmacokinetics

In patients with solid tumors administered single and multiple doses of lenvatinib once daily, the maximum lenvatinib plasma concentration (Cmax) and the area under the concentration-time curve (AUC) increased proportionally over the dose range of 3.2 mg (0.1 times the recommended clinical dose of 24 mg) to 32 mg (1.33 times the recommended clinical dose of 24 mg) with a median accumulation index of 0.96 (20 mg) to 1.54 (6.4 mg).

Absorption

The time to peak plasma concentration (Tmax) typically occurred from 1 to 4 hours post-dose.

Food Effect: Administration with a high fat meal (approximately 900 calories of which approximately 55% were from fat, 15% from protein, and 30% from carbohydrates) did not affect the extent of absorption, but decreased the rate of absorption and delayed the median Tmax from 2 hours to 4 hours.

Distribution

In vitro binding of lenvatinib to human plasma proteins ranged from 98% to 99% at concentrations of 0.3 to 30 µg/mL. The blood-to-plasmconcentration ratio ranged from 0.59 to 0.61 at concentrations of 0.1 to 10 µg/mL in vitro.

Elimination

The terminal elimination half-life of lenvatinib was approximately 28 hours.

Metabolism: The main metabolic pathways for lenvatinib in humans were identified as enzymatic (CYP3A and aldehyde oxidase) and non-enzymatic processes.

Excretion: Ten days after a single administration of radiolabeled lenvatinib, approximately 64% and 25% of the radiolabel were eliminated in the feces and urine, respectively.

9.1.8 Drug Interactions

Effect of Other Drugs on Lenvatinib

CYP3A, P-gp, and BCRP Inhibitors: Ketoconazole (400 mg daily for 18 days) increased lenvatinib (administered as a single 5 mg dose on Day 5) AUC by 15% and Cmax by 19%. P-gp Inhibitor: Rifampicin (600 mg as a single dose) increased lenvatinib (24 mg as a single dose) AUC by 31% and Cmax by 33%.

CYP3A and P-gp Inducers: Rifampicin (600 mg daily for 21 days) decreased lenvatinib (24 mg as a single dose on Day 15) AUC by 18%. The Cmax was unchanged.

In Vitro Studies with Transporters: Lenvatinib is a substrate of P-gp and BCRP but not a substrate for organic anion transporter (OAT) 1, OAT3, organic anion transporting polypeptide (OATP) 1B1, OATP1B3, organic cation transporter (OCT) 1, OCT2, multidrug and toxin extrusion (MATE) 1, MATE2-K, or the bile salt export pump (BSEP).

Effect of Lenvatinib on Other Drugs

Clinical Studies with Substrates of CYP3A4 or CYP2C8: There is no projected significant drug-drug interaction risk between lenvatinib and midazolam (a CYP3A4 substrate) or repaglinide (a CYP2C8 substrate).

In Vitro Studies with Substrates of CYP or UDP-glucuronosyltransferase (UGT): Lenvatinib inhibits CYP2C8, CYP1A2, CYP2B6, CYP2C9, CYP2C19, CYP2D6, and CYP3A. Lenvatinib does not inhibit CYP2A6 and CYP2E1. Lenvatinib induces CYP3A, but it does not induce CYP1A1, CYP1A2, CYP2B6, and CYP2C9.

Lenvatinib inhibits UGT1A1, UGT1A4, and UGT1A9 in vitro, but likely only inhibits UGT1A1 in vivo in the gastrointestinal tract based on the expression of the enzyme in tissues. Lenvatinib does not inhibit UGT1A6, UGT2B7 or aldehyde oxidase. Lenvatinib does not induce UGT1A1, UGT1A4, UGT1A6, UGT1A9, or UGT2B7.

In Vitro Studies with Substrates of Transporters: Lenvatinib does not have the potential to inhibit MATE1, MATE2-K, OCT1, OCT2, OAT1, OAT3, BSEP, OATP1B1, or OATP1B3 in vivo.

Lenvatinib has been reported to prolong the QT/QTc interval. Avoid coadministration of lenvatinib with medicinal products with a known potential to prolong the QT/QTc interval.

